1.0 Objectives

1.1 Study Objectives

Aim: To determine the effect of varying the energy density of foods served over five days on energy intake in preschool children.

Hypotheses:

1. Mean daily energy intake will be greater when children are served higher-energy-dense versions of foods over five days than when they are served lower-energy-dense versions of the same foods over five days.
2. Daily energy intake in the conditions with higher and lower energy density will begin to converge across the 5-day period.
3. Energy intake across the 5-day period will be adjusted closer to baseline in response to decreases in energy intake than in response to increases in energy intake.

1.2 Primary Study Endpoints

1. Daily intake of food and beverages by energy (kilocalories)

1.3 Secondary Study Endpoints

2. Daily intake of food and beverages by weight (grams)
3. Daily intake of food and beverages by energy density (kilocalories/gram)

2.0 Background

2.1 Scientific Background and Gaps

It has been proposed that preschool children are in a formative stage during which the ability to regulate energy intake is being replaced by eating in response to environmental food cues. In recent studies [1-4], we have found that increases in both food portion size and energy density have been robust in promoting excess energy intake in preschool children over one to two days. These results challenge the proposition that preschool children show self-regulatory behavior by altering their energy intake when it is perturbed by variations in the available foods.

At present, no controlled studies have been conducted over a sufficient duration, estimated to be three to four days, to determine whether children adjust energy intake in response to differences in energy density in the eating environment.

2.2 Previous Data

See references 1 through 4

2.3 Study Rationale

This study will allow us to investigate preschool children's ability to regulate their energy intake and to assess how energy density affects intake over a longer period of time.

3.0 Inclusion and Exclusion Criteria

3.1 Inclusion Criteria

1. Children enrolled in one of the participating child care centers
2. Children who are between the ages of 3 and 5 years old at the time of enrollment
3. Parents (18 years or older) of children enrolled in the study
4. Teachers (18 years or older) in a classroom with enrolled children

3.2 Exclusion Criteria

1. Children with allergies or restrictions to any of the foods served
2. Children with health issues that preclude participation
3. Children who are unavailable for the entire duration of the study

3.3 Early Withdrawal of Subjects

3.3.1 Criteria for removal from study

There are no criteria for removal of subjects from the study. All participation is voluntary and a child can refuse a meal session and parents may withdraw from the study at any time.

3.3.2 Follow-up for withdrawn subjects

N/A

4.0 Recruitment Methods

4.1 Identification of subjects

Any child and parent in a participating classroom of the child care center may participate. Teachers of participating children in the classroom will also be asked to participate.

4.2 Recruitment process

We will recruit through a parent letter placed in each child's mailbox. A study staff member who is approved (in this application) to do recruitment and consenting of subjects will be available in the center during child pick-up to answer any questions parents may have.

Teachers in classrooms will be verbally asked to participate by study staff.

4.3 Recruitment materials

Parents will receive a letter in their child's mailbox that will describe the study. The consent form will be included with the letter.

Teachers in classrooms will be verbally asked to participate by study staff. A consent form will then be reviewed and signed by each teacher willing to participate.

4.4 Eligibility/screening of subjects

Children with allergies or restrictions to the foods served in the study will not be eligible to participate. Screening questions regarding food allergies and intolerances will be included with the consent form.

5.0 Consent Process and Documentation

5.1 Consent Process

5.1.1 Obtaining Informed Consent

5.1.1.1 Timing and Location of Consent

Consent will be signed by the parent. Consent will be obtained at the child care center by a trained member of the study staff.

Teachers will consent to fill out a questionnaire about enrolled children prior to the first study week in their classroom at the child care center.

An addendum consent was added to this study due to university closure for inclement weather. Since five consecutive days are needed for data collection, Study Week 2 was restarted for one cohort.

Only parents will be given the consent addendum as teacher participation does not change with this rescheduling. Parents will be given the addendum at the child care center. Consent will be obtained at the child care center by a trained member of the study staff.

5.1.1.2 Coercion or Undue Influence during Consent

Parents will be given the consent form to take home to review on their own and can decide if they want their child to participate.

Teachers will be given the opportunity to review the consent form on their own and can decide if they wish to participate.

5.1.2 Waiver or alteration of the informed consent requirement

N/A

5.2 Consent Documentation

5.2.1 Written Documentation of Consent

Participation in this study is voluntary. Participation in the changed schedule is voluntary.

A parent of the participant will sign the consent form. Parents will be given a copy of the consent form to keep for records.

A parent of the participant will sign the consent addendum. Parents will be given a copy of the consent addendum to keep for their records.

Teachers will sign a separate consent form for their participation and will be given a copy for their own records.

5.2.2 Waiver of Documentation of Consent

N/A

5.3 Consent – Other Considerations

5.3.1 Non-English Speaking Subjects

It is not anticipated that there will be any non-English speaking or illiterate subjects.

5.3.2 Cognitively Impaired Adults

5.3.2.1 Capability of Providing Consent

N/A

5.3.2.2 Adults Unable To Consent

N/A

5.3.2.3 Assent

N/A

5.3.3 Subjects who are not yet adults (infants, children, teenagers)

5.3.3.1 Parental Permission

Parents will sign consent for their child to participate.

5.3.3.2 Assent

Children can refuse to eat any meal if they choose. Before height and weight are measured or the Tasting Game occurs, children are asked if they want to do it and can refuse to participate.

6.0 Study Design and Procedures

6.1 Study Design

This crossover study has a within-subjects design. There will be three experimental conditions; one condition in which meals of lower energy density (ED) are served, one condition in which meals of baseline energy density are served, and one condition in which meals of higher energy density are served. The order of conditions across the three 5-day periods will be counterbalanced across classrooms. Children will be served the same amount (weight) of food and beverages across all three conditions. In the lower-ED condition, the amount of energy served over each day is ~225 calories less than in the baseline condition. Energy served over the day in the higher-ED condition is ~225 calories more than in the baseline condition. Daily menus in all conditions meet the minimum guidelines for energy and food groups outlined by the USDA and the Child and Adult Care Food Program (CACFP).

6.2 Study Procedures

1. Over 5 consecutive days, enrolled children will be served breakfast, lunch, dinner, and snacks of foods commonly served in the child care center according to their regular meal and snack schedules. Study menus were developed from the menus at each child care center to be similar to the foods that children are regularly served. Milk or water will be served as beverages. Meals will be served at tables of 3 to 6 children and one adult, which is a standard practice at the child care centers. The adults at the table will be instructed not to discuss the food or to encourage the children to eat. There will be three experimental conditions, which differ only in food energy density. The lower-energy-density condition will provide foods 20% lower in energy density than the baseline condition, and the higher-energy-density condition will provide foods 20% higher in energy density than the baseline condition. Each participant will be served individual pre-weighed meals. All food and beverage items will be weighed with a food scale before and after meals to within 0.1 grams in order to determine the amount consumed. Participants will be told they can eat as much or as little of the foods as they would like. Trained study staff will document food and beverage spillage and any comments made about the food. The children will be provided with an evening snack pre-packaged for consumption at home. Any leftover food from the evening snack will be returned to the child care center the following day to be weighed.

2. Parents will be asked not to serve any additional food or beverages to their child apart from those provided by the study and water. If there is any deviation from this procedure, parents will be asked to report the extra food and beverage consumption.
3. Physical activity levels will be measured using tri-axial accelerometers worn over the five study days in each period. The accelerometers will be worn while the children are present at the child care center (from before breakfast to after dinner). Study staff will attach a device to the child's waist upon arrival at the center each morning and remove the device upon the child's departure from the center each evening.
4. On the final (16th) visit to the child care center, children will have their height and weight measured by a trained member of the study staff. Body weight will be measured in triplicate using a portable digital scale, and height will be measured in triplicate using a portable stadiometer. The children will also complete the Tasting Game, in which they are asked to taste a small food sample and point to a cartoon face that represents their liking of the food on a scale of "yucky" to "yummy".
5. Parents will be asked to complete an Evening Report form, Background Questionnaire, Children's Eating Behavior Questionnaire, Caregiver's Feeding Style Questionnaire, and Child Feeding Questionnaire. The Evening Report form will be completed at the end of each study day and returned each morning to study staff. The Background Questionnaire will be completed during the first 5-day study period and returned to study staff. The Children's Eating Behavior Questionnaire, Caregiver's Feeding Style Questionnaire, and Child Feeding Questionnaire will be administered during the last 5-day study period. All questionnaires will be completed using paper copies.
6. Photographs may be taken of children eating meals, participating in the Tasting Game, or having their height and weight measured.
7. There will be a 1-week break between 5-day study periods. There will be a 4- to 6-week wash-out period between this experiment and Experiments 1 and 3 at each child care center. We will rotate the participating child care centers to ensure that each child completes the wash-out and is eligible to participate in the next experiment if they choose.
8. Approved study staff (on this application) will email parents on the Friday before a study week begins to remind parents of the upcoming study week.
9. Teachers will be asked to complete one questionnaire (Caregiver's Feeding Style Questionnaire) per participating child in their classroom. Teachers will only complete questionnaires about children who are enrolled in the study. This questionnaire will be administered using a paper copy. Teachers will be verbally informed by study staff about the children for whom they are to complete questionnaires.
10. Data from questionnaires completed by teachers will be linked to child participants by a three digit number and letter only.

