8.0 Statistical Plan

8.1 Sample size determination

The sample size for the study was estimated from a linear mixed model and an approximation technique [5] using exemplary data sets based on prior 1- and 2-day studies in preschool children [2,3]. We assessed the required sample size for several scenarios with different assumptions about changes in intake on days 3 to 5 that represented quadratic trajectories over time. To detect a clinically significant change of 50 kcal/d over time (movement toward adjustment after 3 to 5 days) with a Type 1 error rate of 5% and power of 90%, it was determined that 45 participants would be required. To allow for withdrawals and non-compliance to the protocol, at least 55 children will be enrolled.

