The influence of continuous participant characteristics (age, body weight, height, BMI-for-age percentile, BMI z-score, step counts, and questionnaire subscales) on the relationship between the experimental factors and intake is assessed by analysis of covariance with linear mixed models. Because multiple participant characteristics are tested as covariates, the method of Benjamini and Hochberg [6] is used to adjust the significance levels, with the false discovery rate set at 0.05 [6]. In order to standardize for energy needs, models having significant covariance with weight status are adjusted for estimated energy requirements [7]. Differences in subject characteristics between boys and girls, as well as differences in intake between children with and without obesity (sex-specific BMI-for-age percentile ≥ 85 and < 85 , respectively), are assessed by independent-samples t-tests. Within conditions, the means of daily energy intakes expressed as a percentage of estimated energy requirements are compared to 100% using a one-sample t-test and controlling the family-wise error rate using the Bonferroni correction.

It has been predetermined that children who have incomplete intake measures on ≥ 3 days in all 3 conditions will be excluded from analysis. It has also been predetermined that children who eat $> 95\%$ of the food weight served on at least 1 day will be classified as "plate cleaners", and their influence on the results will be tested. To evaluate whether the distribution of taste ratings (yummy, just okay, yucky) of the lunch and snack dishes differs significantly across experimental conditions, ordinal logistic regression is used; results are reported as odds ratios (OR) with 95% confidence intervals. Outcomes from

statistical models are reported as mean \pm SEM and subject characteristics are reported as mean \pm SD. Standardized effect sizes are calculated using Cohen's d statistic, with no adjustment for correlation due to repeated measures. Results are considered significant at $P < .05$. All data are analyzed using SAS software (SAS 9.4, SAS Institute, Inc., Cary, North Carolina, USA).

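### Height and weight are first measured at the final visit, so a child who leaves early but stays in the analysis has no BMI or energy requirement for the secondary analyses

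*Combined protocol and SAP*

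**What the plan says.** Section 6.2, item 4, places the only height and weight measurement after all the feeding days: "On the final (16th) visit to the child care center, children will have their height and weight measured by a trained member of the study". The Tasting Game is held at the same visit. No section schedules an earlier measurement or one at withdrawal.

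Section 8.2 relies on these values in several places. It plans to assess "The influence of continuous participant characteristics (age, body weight, height, BMI-for-age percentile, BMI z-score, step counts, and questionnaire subscales" as modifiers of the effect of the experimental factors on intake. It splits children into two weight-status groups by BMI percentile and compares their intake. It adjusts for estimated energy requirement in models where weight status is a significant covariate. It also expresses intake as a percentage of that requirement and tests the mean against 100% within each condition.

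The exclusion rule in 8.2 is that "children who have incomplete intake measures on ≥ 3 days in all 3 conditions will be excluded from analysis". Section 8.1 expects some loss: "To allow for withdrawals and non-compliance to the protocol, at least 55 children will be enrolled". Section 3.3.1 lets parents withdraw at any time, and 3.3.2 marks follow-up of withdrawn children as not applicable. Under 5.3.3.2 a child may decline to be measured.

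**The concern.** The rule for who is analysed and the schedule for measuring body size do not fit together. A child can meet the rule on the strength of one or two periods and still never reach the one visit that supplies weight, height and BMI. That child counts in the unadjusted intake models and is absent from the BMI covariate models, the weight-status contrast, the comparison with 100% of energy requirement and any requirement-adjusted model. Section 8.2 gives no method for missing covariates, so the analysed set would change from one model to the next without the plan saying so. A difference between the adjusted and unadjusted results could then reflect the adjustment, the change of children, or both.

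A single occasion at the end is also fragile for children who stay. One who completes all 15 feeding days but is absent or declines at the 16th visit loses the same values.

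**Working it through.** **Inputs.** Three periods of five days and a 16th visit (6.2, 6.3); 45 children required and at least 55 enrolled (8.1); the exclusion rule (8.2); a 1-week break between periods (6.2, item 7).

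**1. Timing.** 3 × 5 + 1 = 16, so the measurement follows every feeding day. Three study weeks and two break weeks put it about five weeks after the start.

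**2. Who the rule keeps.** Take a child with complete intake data until leaving, and count every later study day as incomplete.

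| Child leaves after | Incomplete days, periods 1 / 2 / 3 | Literal reading: excluded only if ≥ 3 in each condition | Pooled reading: excluded if ≥ 3 in total |
|---|---|---|---|
| Period 1 | 0 / 5 / 5 | kept | excluded (10) |
| Period 2 | 0 / 0 / 5 | kept | excluded (5) |
| Day 3 of period 3 | 0 / 0 / 2 | kept | kept (2) |
| Day 5 of period 3, misses 16th visit | 0 / 0 / 0 | kept | kept (0) |

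On the literal reading, two or fewer incomplete days in any one condition are enough to stay in. A child who left after day 3 of period 1 (2 / 5 / 5) would therefore be kept. On the pooled reading, the mismatch is confined to children lost in the last two or three days and those not measured at the 16th visit.

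**3. How many.** The required 45 cannot be reproduced, because 8.1 gives no standard deviation, correlation or trajectory. It is not in dispute here and serves only to set the scale. The allowance is 55 - 45 = 10, and 10 / 55 = 18.2%. If 5 children left early (assumed), 5 / 55 = 9.1%. If 3 did (assumed), 3 / 55 = 5.5%.

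**4. Cost in precision.** Assume one value per child and independent children. The standard error of a between-child association grows by √(55 / n). The correlation detectable with 90% power at two-sided 5% is tanh[(1.960 + 1.282) / √(n - 3)].

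| Children with body size, n | Missing | Standard-error ratio | Detectable correlation |
|---|---|---|---|
| 55 | 0% | 1.00 | 0.42 |
| 50 | 9.1% | 1.05 | 0.44 |
| 45 | 18.2% | 1.11 | 0.46 |

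Even at the ceiling the loss of precision is modest. The change of analysed set between models matters more.

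**5. What is not touched.** The base model in 8.2 has condition, week, day, menu, classroom and sex as fixed factors and participant as a random effect. The convergence models add polynomial terms in time. None needs body size. Age is an enrolment criterion (3.1), and step counts come from accelerometers worn in every period (6.2, item 3), so those two covariates are also unaffected.

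**The case against.** The strongest reply is that the mismatch rests on one reading of the exclusion rule. If incomplete days are counted across the three conditions together, nearly every early leaver is excluded from all analyses and the sets almost coincide. This stands as a limit on size. The literal wording still supports the other reading, and neither reading helps a child who is not measured at the last visit.

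Second, all three hypotheses in 1.1 can be tested without body size, and the energy-requirement adjustment is conditional. This also stands: a reader might infer that the main result is compromised, and the documents do not support that.

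Third, the exclusion in 3.2 of children unavailable for the whole study should reduce early leaving. It does, but 8.1 still plans for withdrawals. Section 5.1.1.1 also records that one cohort's second study week was restarted under a further voluntary consent, which gave parents a point at which to leave. The documents do not say whether any did.

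A reader might extend the point to the three parent eating and feeding questionnaires, which "will be administered during the last 5-day study period", and argue that their scores carry an imprint of the last condition. Nothing in the documents supports such an imprint. Every completer receives all three conditions, order is counterbalanced by classroom, and classroom is in the model. Early leavers would lack these scores too, but their timing is a trade-off. Parents oversee the evening snack at home and report extra foods, so feeding questions asked early could influence what they do. Height and weight carry no such risk.

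Nor can it be assumed that children who refuse meals are the ones missing. Under 3.3.1 a child may refuse a meal session without leaving, and so can still reach the final visit.

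**Conclusion.** The point holds as an inexpensive improvement to the secondary analyses. On the literal reading of the exclusion rule, up to 10 of 55 children (18%) could have intake data but no weight, BMI or energy requirement. That figure is an upper bound, not an expected rate: the allowance also covers non-compliance, non-compliant children who stay are still measured, and a child who leaves before giving usable intake data creates no mismatch. On the pooled reading the number is much smaller.

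The effect falls on the weight, height and BMI covariate models, the weight-status contrast, the comparison with 100% of energy requirement, and any requirement-adjusted intake model. It does not fall on every covariate model, or on the primary comparison and convergence models as specified without covariates.

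Two assumptions remain. That the energy requirement needs measured weight or height is inferred from its use to standardise for energy needs; the equation is cited but not printed. That timing matters little for the values themselves is a judgement: the served-energy difference from baseline is about 225 × 5 = 1,125 kcal per period, and about five weeks is short for growth. The case therefore rests on missing values, not on bias from measuring late.

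**What to change.** In 6.2, item 4, take the same triplicate height and weight measurement on a study day in the first 5-day period. Doing so by the third day would cover the earliest leavers whom the literal rule could keep. Keep the 16th visit for the Tasting Game, and for height and weight only in children who refused or were absent earlier. In 8.2, state that these values are used for BMI and for the energy requirement.

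The cost is a small scheduling change with no added procedure, and body size is recorded about five weeks earlier than now planned. Staff are already at the center on every study day, and first-period collection is already in use for parents: "The Background Questionnaire will be completed during the first 5-day study period and returned to study staff". The parent eating and feeding questionnaires can stay where they are.
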